7.1.4 Eligibility criteria for treatment

Participants who have a quantifiable HCV RNA will be assessed for treatment eligibility. Those in the point-of-care arm will be able to complete the treatment work-up on the day of HCV screening. Those in the control arm and dried blood spot arm will have treatment work-up as per standard of care once the HCV RNA test results are received from the laboratory.

Treatment uptake is expected to be higher at 12 weeks following enrolment in the point-of-care arm (45%) compared with the dried blood spot arm (20%) or control arm (10%).

7.1.4.1 Inclusion criteria

Participants are eligible for HCV DAA treatment if all of the following inclusion criteria are met:

- a. Quantifiable HCV RNA at screening
- b. An assessment of liver cirrhosis status is performed in the intervention arm, i.e. point-of-care and dried blood spot arm:
- i) If pathology is available to determine an APRI in the previous 12 months, and is <1.0, then a FibroScan is not required.

OR

- ii) If pathology is not available for APRI, and no FibroScan is available, then phlebotomy can be taken at baseline and treatment commenced. Once pathology is returned, if >1.0 then an ultrasound can be organised. In these cases (unknown stage of disease) would be preferable to use SOF/VEL, given standard duration.
- c. In the opinion of the Investigator, the participant is suitable for treatment within an NSP-based setting.

7.1.4.2 Exclusion criteria

Participants are not eligible for HCV DAA treatment if any of the following exclusion criteria are met:

- a. In the opinion of the Investigator, any factors or reasons which could preclude management within an NSP-based setting
- Any clinically significant condition or history known to contraindicate the use of the prescribed DAA treatment medication or would not be suitable for management within an NSP-based setting
- c. Any medication contraindicated to the prescribed HCV DAA treatment regimen (as detailed in the product information)
- d. HIV co-infection*
- e. Active hepatitis B co-infection*
- f. Is female and is pregnant or breastfeeding.

HCV RNA negative participants will have no further assessments or visits as part of the study protocol. Participants who are HCV RNA positive will be enrolled in the cohort. Screening in the intervention arm will continue until a total of 220 HCV RNA positive participants (~20 participants per site) are enrolled in the intervention arm (either dried blood spot and point-of-care). In the delayed intervention arm, 220 HCV RNA positive participants (~20 participants per site) will be enrolled in the control (standard of care) phase and then clusters/sites will be switched to intervention (either dried blood spot and point-of-care) – at which screening will continue until a

total of 220 HCV RNA positive participants (~20 participants per site) are enrolled. Hence a total of 660 HCV RNA positive participants will be enrolled in the study.

Participants with a quantifiable HCV RNA will be assessed for treatment based on standard eligibility criteria for government reimbursement of therapy. If eligible, they will be treated as per standard of care with a government approved pan-genotypic HCV DAA treatment. Participants will be encouraged to take the first dose on the day of treatment work-up where possible. On-treatment and post-treatment testing and monitoring will be based on the site investigator as per standard clinical practice.

All HCV RNA positive participants will be followed up at 12 weeks, 24 weeks, and 12 months post HCV RNA test.

9.0 Treatment of participants

9.1 Treatment

Participants (with a quantifiable HCV RNA) who are eligible for treatment will be prescribed a government approved pan genotypic DAA HCV treatment (e.g. glecaprevir/pibrentasvir 300mg/120mg, sofosbuvir/velpatsvir 400mg/100mg, or sofosbuvir/velpatasvir/voxilaprevir 400mg/100mg/100mg), at the discretion of the Investigator. The dose, form, strength, regimen and duration of treatment will be as per the approved product information for the prescribed regimen.

Dispensing

Participants who initiate treatment through the study will be prescribed through a government approved scheme. Participants will collect their medication from a local community pharmacy. Quantities dispensed to participants from the pharmacy and dosing regimen (e.g. daily observed, self-dosed etc.) will be based on the government guidelines and the Investigator's discretion respectively. Details on the HCV treatment administration, including the treatment regimen and date of the first treatment dose and the last treatment dose will be recorded for all HCV RNA positive participants.

9.2 Prior and concomitant medications

Allowed and excluded medications prior to, during the study and post-treatment will be based on the product information of the prescribed HCV DAA therapy as only government approved medicines are used in this study. The treating Investigator will review the participants medical history and review all medication the participant is taking for potential drug-drug interactions. The hep-drug interactions website may be used as a tool: https://www.hep-druginteractions.org/.

10.0 Study procedures

The following assessments must be conducted at study visits as per the schedule of assessments:

	Behavioural survey, Abbreviated behavioural survey, Health outcomes
Questionnaires	survey (EQ-5D-5L), Health economics survey, Testing acceptability
	survey
HCV RNA	HCV RNA via point-of-care, dried blood spot or standard of care*
HIV serology	HIV Ab (point-of-care and dried blood spot arm only)**
HBV serology	HBsAg (point-of-care and dried blood spot arm only)**
Fibrosis assessment	FibroScan or APRI score (point-of-care and dried blood spot arm only)
Dried blood spot	Dried blood spot research sample collection

^{*}For standard of care, participants will be referred for HCV testing, including HCV Ab and/or RNA.

10.1 Screening visit

The following procedures will be completed at the screening visit:

- Informed consent
- Screening behavioural questionnaire
- Health outcomes survey (EQ-5D-5L) and health economics questionnaire
- Testing acceptability questionnaire (control arm only)
- HCV RNA using dried blood spot or point-of-care
 - Dried blood spot: A finger-stick capillary whole blood sample will be collected on a dried blood spot card, air dried for 4 hours and then posted to St Vincent's Hospital Centre for Applied Medical Research (AMR) laboratory for HCV testing. If an invalid or error result is obtained, a repeat test will be performed via venepuncture.
 - O Point-of-care: A finger-stick capillary whole blood sample will be collected for the GeneXpert. Results are generated in approximately 1 hour and provided to the participants on the same day (where possible). If an invalid or error result is obtained, a repeat point-of-care test will be performed (same day where possible).
- HCV testing using standard of care the participant will be referred for HCV testing via standard of care.
- Research blood sample dried blood spot
- HIV and HBV serology using a rapid test for participants with a quantifiable HCV RNA in the intervention arm who initiate HCV treatment. Excluded for those with a recent known status
- Fibrosis assessment for HCV RNA positive participants in the intervention arm only.
- Participant reimbursement

10.2 HCV RNA test notification

Participants at sites randomized to standard of care or dried blood spots will be notified once their results are returned from the testing laboratory whilst those at sites randomized to point-of-care will be notified of their results on the same day (where possible).

Negative results from dried blood spot HCV RNA testing will be delivered through a text message. Participants with a positive result from dried blood spot HCV testing will be notified through a text message to contact the study site team to facilitate the participant to return to the site for HCV RNA results and linkage to care. Positive HCV RNA results will be delivered in person by the site study team.

To facilitate participant notification of results, contact details (phone number and/or email, if available) will be collected through an electronic data capture system. Up to 3 secondary contact

^{**}At time of treatment initiation and excluded for those with a recent known status.

details (phone number and/or email) will be collected in case the study team cannot reach the study participant on their main contact details.

10.3 Registration

Consecutive HCV RNA positive participants will be enrolled in the cohort.

In the intervention arm, screening will continue until a total of 220 HCV RNA positive participants (~20 participants per site) are enrolled in either dried blood spot and point-of-care. Only HCV RNA positive participants i.e., participants with a quantifiable HCV RNA will be followed up after enrolment at 12 weeks, 24 weeks and 1 year.

In the delayed intervention arm, 220 HCV RNA positive participants (~20 participants per site) will be enrolled in the control (standard of care) phase and managed as per site standard of care. Sites will then be switched to intervention (either dried blood spot and point-of-care) – at which screening will continue until a total of 220 HCV RNA positive participants (~20 participants per site) are enrolled. Only HCV RNA positive participants i.e., participants with a quantifiable HCV RNA in the point-of-care or dried blood spot arm will be followed up post-enrolment at 12 weeks, 24 weeks and 1 year.

Hence a total of 660 HCV RNA positive participants.

HCV RNA negative participants will not complete any further visits as part of the study protocol.

10.4 Treatment

Participants with a quantifiable HCV RNA will be assessed for treatment eligibility. If eligible, they will be offered treatment via standard clinical practice as recommended by the Australian recommendations for the management of HCV virus infection: a consensus statement (latest version). Participants will attend at a minimum, a visit prior to treatment and a Week 8-12 post-treatment (SVR).

There are no study specific assessments required during the HCV treatment. The following participant information will be collected through participant medical records/notes for study data:

- Planned duration of treatment
- HCV treatment regimen prescribed
- HCV treatment start and end date
- Treatment outcome (sustained virological response at 12 weeks after the last dose of treatment)

If a participant fails treatment, additional information may be recorded: reason for treatment failure, reinfection risks and reasons for missed doses (if known).

If determined by the doctor to be eligible for treatment initiation a government approved prescription for a pan-genotypic HCV DAA treatment will be provided to the participant (or faxed to their pharmacy). The dose, form, strength, regimen and duration of treatment will be as per the approved product information for the prescribed regimen.

10.5 Follow-up phase

All HCV RNA positive participants i.e., participants with a quantifiable HCV RNA in the intervention arm only will return for follow-up visits at 12 weeks, 24 weeks and 12 months (52 weeks) post-test. The following procedures will be conducted at follow-up visits:

- Follow-up behavioural questionnaire
- Health outcomes survey (EQ-5D-5L) and health economics questionnaire

- HCV RNA (either dried blood spot or point-of-care)
- Participant reimbursement

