4.2 Secondary objective(s)

Among those who receive point-of-care HCV RNA testing, dried blood spot testing, and standard of care:

- 1. To compare the time to HCV DAA treatment initiation among those who initiate treatment.
- 2. To compare the proportion of HCV RNA positive participants who initiate HCV DAA treatment at 24 weeks following enrolment.
- 3. To compare the proportion of HCV RNA positive participants who initiate HCV DAA treatment at 12 months (52 weeks) following enrolment.
- 4. To compare the proportion of participants who complete HCV DAA treatment.
- 5. To compare the proportion of participants who achieve an SVR (defined as HCV RNA below the lower limit of quantitation at post treatment week 12).
- 6. To compare the proportion of participants who are HCV RNA negative at 12 weeks.
- 7. To compare the proportion of participants who are HCV RNA negative at 24 weeks.
- 8. To compare the proportion of participants who are HCV RNA negative at 12 months (52 weeks).
- 9. To evaluate the incidence of HCV reinfection following successful HCV therapy.
- 10. To compare the cost-effectiveness of these different testing strategies.

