10.7 Study questionnaires

All participants will complete behavioural questionnaires, health economics, health outcomes survey (EQ-5D-5L) and testing acceptability questionnaire at Screening. Subsequently, all HCV RNA positive participants in the intervention arm will complete study questionnaires at Follow-up visits 1, 2 and 3.

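### Secondary objectives 6 to 8 compare HCV RNA negativity with standard of care, but no RNA test after week 0 is scheduled for control-phase participants, and section 8.1 conflicts with sections 10.3 and 10.5

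*Protocol*

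**What the plan says.** Protocol section 4.2 opens its list of ten secondary objectives with the groups concerned: "Among those who receive point-of-care HCV RNA testing, dried blood spot testing, and standard of care". Objective 6 is "To compare the proportion of participants who are HCV RNA negative at 12 weeks"; objectives 7 and 8 repeat it at 24 weeks and at 12 months. Objective 9 concerns reinfection after successful therapy. Objective 10 is "To compare the cost-effectiveness of these different testing strategies".

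Section 8.1 gives follow-up without restriction by arm: "All HCV RNA positive participants will be followed up at 12 weeks, 24 weeks, and 12 months post HCV RNA test".

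Four other places restrict it:

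- Section 10.5: "participants with a quantifiable HCV RNA in the intervention arm only will return for follow-up visits at 12 weeks, 24 weeks and 12 months".
- Section 10.3, on the delayed arm: control-phase participants "will be enrolled in the control (standard of care) phase and managed as per site standard of care", and only those "in the point-of-care or dried blood spot arm will be followed up post-enrolment at 12 weeks, 24 weeks and 1 year".
- Section 10.7: "all HCV RNA positive participants in the intervention arm will complete study questionnaires at Follow-up visits 1, 2 and 3".
- Schedule 1.3.2 (control): only a screening and a registration column, both at study week 0. Schedule 1.3.1 (intervention) has RNA tests, EQ-5D-5L and the health economics questionnaire at weeks 12, 24 and 52.

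**The concern.** A three-way comparison of RNA negativity needs an RNA result at the stated times in all three groups. The plan schedules one in two of them. Any standard-of-care figure for objectives 6 to 8 would therefore come from whichever controls happened to be tested in routine care or on re-screening. The comparison would then partly reflect who was measured and not the testing strategy. An analysis plan can choose a method, but it cannot supply results that the protocol does not collect.

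The conflict with section 8.1 adds a practical risk: a site that works from 8.1 would follow control participants differently from a site that works from 10.3 or 10.5.

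**Working it through.** **1. Size of the groups.** Section 6.0 gives three blocks of RNA positive participants: immediate intervention, control phase, and the delayed arm after switching. Each block is 11 sites × about 20 = 220, and 3 × 220 = 660, which is the protocol's own total. Control phase: 220/660 = 33.3%. Intervention phases: 440.

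**2. Scheduled RNA tests after week 0.** Weeks 12, 24 and 52: all 440 intervention-phase participants, and none of the 220 control-phase participants.

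**3. Whether another planned source fills the gap.**

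- *Treatment records (sections 9.1 and 10.4).* Treatment details are recorded for every RNA positive participant, and SVR is taken from medical records with no restriction by arm. This reaches treated controls only. Section 14.3 expects 10% uptake by week 12: 220 × 0.10 = 22. The same arithmetic gives 220 × 0.20 = 44 and 220 × 0.45 = 99 in the other arms, and 22 + 44 + 99 = 165, as the protocol states. That leaves 220 − 22 = 198 controls (198/220 = 90%) with no planned later RNA result.
- *Timing of SVR.* SVR is counted from the end of treatment, not from enrolment. Section 10.4 puts the post-treatment visit at 8 to 12 weeks, and the week-12 window in schedule 1.3.1 closes at week 14. An SVR result can fall inside that window only if treatment has ended by week 14 − 8 = 6. The protocol gives no treatment durations, so this is conditional, but it leaves little or nothing for objective 6.
- *Research dried blood spot.* Schedule 1.3.2 has it at screening only.
- *Re-screening (section 10.6).* Untreated controls may be re-screened in the intervention phase from 3 months. That test comes before any intervention-phase treatment, so it does say something about status at about that time. It is optional, excludes treated controls and depends on re-attendance. Once re-screened, the participant has entered the intervention, so later results are not standard-of-care outcomes at 24 or 52 weeks.
- *Data linkage (section 10.7.4).* It is optional, and the variables listed include neither RNA results nor EQ-5D-5L.

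**4. What the records alone could say about control RNA negativity.** Let u be the share of controls treated, and assume 95% cure among them (the protocol's background gives cure rates above 95%). With no result for the rest:

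- lower bound = 0.95u (no untreated control is negative)
- upper bound = 0.95u + (1 − u) (every untreated control is negative)

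The width is 1 − u.

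| Assumed control uptake u | Treated | No planned result | Bounds |
|---|---|---|---|
| 10% (protocol, by week 12) | 22 | 198 (90%) | 20.9/220 = 9.5% to 218.9/220 = 99.5% |
| 45% (protocol's figure for point-of-care, borrowed as an extreme) | 99 | 121 (55%) | 94.05/220 = 42.8% to 215.05/220 = 97.8% |

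The protocol gives no control uptake beyond week 12. The second row shows that the gap stays wide even at the highest uptake it assumes for any arm. These are worst-case limits, not estimates.

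**5. Objective 10.** Controls complete EQ-5D-5L and the health economics questionnaire at screening only. Follow-up utilities and questionnaire costs exist for the intervention phases alone. Treatment starts, SVR from records and, with consent, linked prescription, hospital and MBS/PBS data exist for controls too.

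**The case against.** Leaving standard of care unvisited is a defensible pragmatic choice, because study retesting could change what standard of care is. That stands: the fault lies in how objectives 6 to 8 are worded, not in the decision to leave controls alone.

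The conflict with 8.1 can also be read more softly. That section speaks of being followed up, whereas 10.5 speaks of returning for visits, and records could count as follow-up. This helps against 10.5 but not against 10.3, which uses the same verb and confines it to the point-of-care and dried blood spot groups.

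Section 14.5 does not name RNA negativity or cost-effectiveness among its secondary analyses, and no power figure depends on either. That limits the severity. It does not remove the objectives from section 4.2.

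Four stronger readings are tempting and are not supported:

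- *Cost-effectiveness against standard of care cannot be answered.* Objective 10 promises no particular method, and treatment data, SVR records, consented linkage and modelling remain open. Only a comparison using follow-up EQ-5D-5L and questionnaire costs measured in all groups is lost.
- *There are no control data after screening.* Sections 9.1, 10.4, 10.6 and 10.7.4 provide some. They are partial and selective for RNA negativity.
- *Untested controls would be scored as still positive.* The only such rule, in section 14.5, concerns treatment initiation. Nothing extends it to RNA results.
- *The main result is compromised.* Initiation, completion and SVR come from treatment records and do not depend on these visits.

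**Conclusion.** The point holds for objectives 6 to 8 and for the inconsistency in section 8.1. About 220 of 660 RNA positive participants, one third, have no scheduled RNA measurement after week 0. At the protocol's 10% uptake, 90% of them have no planned later result from any source that covers controls as a group. The comparison with standard of care on RNA negativity cannot be made from the planned data. The bounds rest on the stated uptake and an assumed 95% cure. The absence of scheduled tests rests on the text alone.

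For objective 10 the point is narrower: the protocol does not say where control follow-up data on costs and utilities would come from, although usable sources exist. The primary outcome and objectives 1 to 5 are unaffected. This should be fixed, but it does not threaten the trial's main conclusion.

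**What to change.** 1. Restate objectives 6, 7 and 8 as comparisons of point-of-care with dried blood spot only.
2. Limit objective 9 to the intervention-phase cohorts that are followed.
3. Reconcile the follow-up sentence in section 8.1 with sections 10.3, 10.5 and 10.7 and schedule 1.3.2.
4. Under objective 10, state that follow-up EQ-5D-5L and health economics questionnaire data exist only for intervention-phase participants. Any comparison with standard of care then rests on treatment and SVR records, consented data linkage or modelling. The text should not say that controls have no follow-up data at all, because that would be inaccurate.

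The cost is protocol wording. The sponsor gives up secondary claims on RNA negativity against standard of care that the planned data could not support. No visit, sample size or primary analysis changes.

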10.6 Re-screening

For participants with a quantifiable HCV RNA who do not initiate treatment in the control phase (standard of care) of the delayed intervention arm, they can be re-screened in the intervention phase 3 months after their date of screening.

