1.3.2 Delayed Intervention (Control) Arm

	All participants	All participants will as per site standa	Once clusters/sites are switched, follow		
		Participants with a quantifiable HCV RNA	All other participants	procedures for the Intervention Arm.	
Study Visit	Screening ⁴	Registration ⁵	N/A		
Study Weeks	0	0	N/A		
Visit Window (weeks, min to max)	0	N/A	N/A		
Informed consent	X				
Behavioural questionnaire	X				
(Screening version)					
EQ-5D-5L	X				
Health economics questionnaire	x				
Testing acceptability questionnaire ¹	х				
HCV RNA and/or Ab ²	Х	X			
HCV result notification ³	х	х			
Treatment ⁴		X			
Research Samples					
Dried blood spot	X				

Key	
1	Testing acceptability questionnaire will be completed in the control arm only.
2	Participant will be referred for HCV testing (standard of care).
3	Standard of care arm: The result will be delivered as per site local procedure.
	Refer to section 10.2 for additional details.
4	For participants with a quantifiable HCV RNA who do not initiate treatment in the control
	arm (standard of care), they can be re-screened in the delayed intervention arm 3 months
	after their date of screening.
5	Data will be collected on participants with a quantifiable HCV RNA and those who initiate
	HCV treatment.

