6.0 Participant population

It is anticipated that approximately 3,300 participants (assuming an HCV RNA prevalence of 20%) will be screened for HCV infection using either dried blood spot testing, point-of-care testing or standard of care testing.

Screening in the intervention arm will continue until a total of 220 HCV RNA positive participants (~20 participants per site) are enrolled in the intervention arm (either dried blood spot and point-of-care). In the delayed intervention arm, 220 HCV RNA positive participants (~20 participants per site) will be enrolled in the control (standard of care) phase and then clusters/sites will be switched to intervention (either dried blood spot and point-of-care) – at which screening will continue until a total of 220 HCV RNA positive participants (~20 participants per site) are enrolled. Hence a total of 660 HCV RNA positive participants.

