7.1.3 Exclusion criteria for participants

Attendees of the NSP service are not eligible for inclusion if any of the following exclusion criteria are met:

 a. Is unable or unwilling to provide informed consent or abide by the requirements of the study.

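### Control participants who did not start treatment can be enrolled again in the delayed intervention phase, so entry depends partly on the primary outcome and 24- and 52-week control results can include intervention-driven starts

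*Protocol*

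**What the plan says.** The rule appears twice in the protocol. Section 10.6 says that control-phase participants with quantifiable HCV RNA who did not initiate treatment "they can be re-screened in the intervention phase 3 months after their date of screening". Key 4 of the schedule in section 1.3.2 repeats it: "they can be re-screened in the delayed intervention arm 3 months".

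The enrolment rules set no limit on what follows. Section 10.3 states "Consecutive HCV RNA positive participants will be enrolled in the cohort". For the control phase it says "In the delayed intervention arm, 220 HCV RNA positive participants (~20 participants per site) will be enrolled in the control (standard of care) phase", and after the switch "screening will continue until a total of 220 HCV RNA positive participants (~20 participants per site) are enrolled". The only participant exclusion, in section 7.1.3, is "Is unable or unwilling to provide informed consent or abide by the requirements of the study". Section 6.0 adds the three groups: "Hence a total of 660 HCV RNA positive participants".

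Secondary objective 2 in section 4.2 reads "To compare the proportion of HCV RNA positive participants who initiate HCV DAA treatment at 24 weeks following enrolment", and objective 3 is the same at 52 weeks. Both apply to all three strategies, including standard of care.

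**The concern.** Re-entry is open only to people who did not have the primary outcome at their first enrolment; those who started treatment have no such route. If re-screened people count toward the second 220, the delayed intervention phase is partly made up of known non-initiators, while the immediate intervention arm has none. The before-and-after contrast within delayed sites is the most exposed, and the 660 would be enrolments rather than people.

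The second problem is timing. Three months falls after week 12 but before weeks 24 and 52. A control participant who is re-screened and starts treatment after a point-of-care or dried blood spot test can still be inside the control 24- or 52-week window. Such starts would be seen: key 5 of section 1.3.2 collects treatment initiation for controls, and section 14.5 treats initiators as traceable. Counted as standard of care, they would shrink the comparison in objectives 2 and 3.

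**Working it through.** **Plan's own figures (section 14.3).** 3 x 220 = 660. Treated: 220 x 10% = 22, 220 x 20% = 44 and 220 x 45% = 99, total 165. These reproduce. With m = 20 and ICC 0.05 the design effect is 1 + 19 x 0.05 = 1.95. Eleven against eleven clusters at 10% vs 30% then give 96.8% power (95.8% using t with 20 df), so the stated 90% is met with room to spare.

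**People exposed to the rule.** Control non-initiators: 220 - 22 = 198, at most 198/220 = 90% of the delayed-phase places and 198/440 = 45% of all intervention places. The protocol gives no return rate or cap, so these are assumptions:

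| Share of the 198 returning | Repeat enrolees | Share of delayed phase | Share of all intervention places | Distinct people |
|---|---|---|---|---|
| 10% | 20 | 9% | 4.5% | 640 |
| 50% | 99 | 45% | 22.5% | 561 |
| 100% | 198 | 90% | 45% | 462 |

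**Primary outcome of controls.** Three months is at least 89 days and 12 weeks is 84 days, so re-screening cannot alter the control 12-week outcome.

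**Shift in intervention uptake.** Planned pooled intervention uptake is (20% + 45%)/2 = 32.5% (section 14.3 uses 30% as its example). Take the strongest selection that the first outcome alone can produce: everyone who would start under standard of care would also start under the intervention, propensity is stable, and returners are representative. Uptake among non-initiators is then (32.5 - 10)/(100 - 10) = 25%, a ratio of 25/32.5 = 0.77. Shift = share of intervention places x (25 - 32.5):
- 10% return: 0.045 x (-7.5) = -0.3 points
- half return: 0.225 x (-7.5) = -1.7 points
- all return: 0.45 x (-7.5) = -3.4 points

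The planned pooled difference is 32.5 - 10 = 22.5 points.

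**Objectives 2 and 3.** No 24- or 52-week rates are given. For illustration only, carry 10% vs 30% forward and let every re-screened person's start fall inside the control window. With 25% re-screened at 15% uptake, control becomes 10 + 0.9 x 0.25 x 15 = 13.4%, and the gap is 16.6 points instead of 20. With 50% re-screened at 30% uptake, control becomes 10 + 0.9 x 0.5 x 30 = 23.5%, and the gap is 6.5 points. The real share depends on when sites switch, which section 8.1 ties to numbers enrolled.

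**Power if repeat enrolees are left out and not replaced (20% vs 45%).** The loss falls only on the 11 delayed sites: (220 - 99)/11 = 11 per site if half return, (220 - 198)/11 = 2 if all return. The effective size of a site is m/(1 + (m - 1) x 0.05): 10.26 for m = 20, 7.33 for m = 11 and 1.90 for m = 2. With 5 or 6 immediate sites in each testing arm:
- half return: 95.3 and 98.2 effective per arm; power about 97% (z) or 95-96% (t)
- all return: 5 x 10.26 + 6 x 1.90 = 62.7 and 6 x 10.26 + 5 x 1.90 = 71.1; SE = sqrt(0.16/62.7 + 0.2475/71.1) = 0.0777; 0.25/0.0777 = 3.22; power about 90% (z) or 86% (t). Weighting by individuals instead gives as low as 84% (t).

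Control versus intervention at 10% vs 30%, using only the immediate arm (220 vs 220, design effect 1.95), stays at about 96-97%.

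**The case against.** The strongest reply is that double counting is inferred from silence. The protocol says these people can be re-screened; it does not say that they fill the second 220, enter the primary analysis, or carry later starts back to their control record. A statistical analysis plan, which is not at hand, could count first enrolments only. That is fair as to the analysis. It does not dispose of recruitment: who fills the places is fixed in sections 6.0, 10.3 and 10.6, and followed literally they admit repeat enrolees. An analysis plan cannot refill places already used.

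The size and direction are also open. People who already know their status might start faster, and section 2.0 attributes drop-off to the multi-visit pathway that the intervention shortens. This stands: a bias toward no effect is likely, not certain.

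A reader might infer a much larger bias by supposing that re-screened people start at 0.3 to 0.7 times the rate of new participants; that would give -2 to -5 points if half return and -4 to -10 if all do. The documents do not support it. Non-initiators are 90% of controls, so selection on the first outcome alone gives a pooled ratio no lower than about 0.77. A reader might also infer invalid standard errors from two records on one person. Robust errors clustered on site cover that correlation when both records are at one site.

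**Conclusion.** The point holds as a defect in a stated rule. Read together, sections 1.3.2, 7.1.3, 10.3 and 10.6 let the primary outcome of one enrolment decide who may enter another, and let one person occupy two of the 660 places. The effect on the primary comparison is modest at the plan's own rates: about -0.3, -1.7 or -3.4 points of pooled intervention uptake at 10%, half or full return, given stable propensity and representative returners. Larger shifts need a further assumption.

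A reader might infer that the control group's primary result is contaminated; it is not. Nor do the documents show that control 24- and 52-week rates will include intervention-driven starts, only that nothing prevents it. That exposure could matter more than the primary shift, but its size depends on return rates and switch dates that the protocol does not give.

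**What to change.** Leave re-screening itself unchanged. In sections 10.3, 10.6 and 14.5, state that each person counts once, by first enrolment, toward the 660 and in the primary analysis. Add an eCRF flag linking the two records, report re-screened people separately, and run a sensitivity analysis that includes them.

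For objectives 2 and 3, choose one of two routes. Either limit the 24- and 52-week contrasts to point-of-care versus dried blood spot, or do not credit starts after re-screening to standard of care and analyse time to initiation with control follow-up censored at re-screening. Censoring alone does not fit the binary analysis in section 14.5, where people lost before starting count as non-initiators, so the second route needs the time-to-event form. Its censoring may be informative, which should be acknowledged.

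The cost is a few sentences, one data field and a smaller delayed intervention phase if repeat enrolees are not replaced. Power for dried blood spot versus point-of-care stays at about 95-97% if half return, but drops to about 84-90% if all return, which can fall below the stated 90%. Replacing them avoids that loss at the price of more screening: at 20% prevalence, 99 replacements need about 99/0.20 = 495 further screens.
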